Title: Treatment of Pressure Ulcers using Biological Skin Substitutes: A Comparison of Type-I Collagen and Amnion/Chorion Membranes

NCT: NCT06853210

Date: 26/07/2025

Background

Pressure ulcers, also known as decubitus ulcers or bedsores, are localized injuries to the skin and underlying tissue resulting from prolonged pressure. They are prevalent in individuals with limited mobility, such as the elderly and those with spinal cord injuries, particularly in long-term care settings. Effective management of pressure ulcers is crucial to prevent complications and improve patient outcomes, includes pressure relief, wound care, and advanced therapies such as bioengineered skin substitutes. Management of pressure sores is crucial due to their association with increased morbidity, healthcare costs, and reduced quality of life. This study aims to evaluate the efficacy of two treatment modalities: Type-I Collagen-based Skin Substitute (HPTC) vs. Dehydrated Human Amnion/Chorion Membrane (dHCAM) in promoting the healing of pressure ulcers. While both products are used in wound management, direct comparative studies evaluating their efficacy in treating pressure ulcers are limited.

MATERIALS AND METHODS

This prospective, randomized, controlled, open label, two parallel group, single-centre clinical trial will be conducted at a tertiary care hospital, in India, specializing in wound care and reconstructive surgery. The study protocol was approved by the Institutional Ethics Committee (Approval Number: AIMS/IEC/012/2025) and pre-registered with the ClinicalTrials.gov (NCT06853210). All procedures will be performed in accordance with the Declaration of Helsinki and Good Clinical Practice guidelines. All participants or guardians will be provided informed consent.

Outcome Measures

Primary Outcome:

- a. Percentage Wound Area Reduction.
- b. Histopathological Parameters
 - i. Vascular Infiltration
 - ii. Neo-epithelialization
 - iii. Fibroblast Activity
 - iv. Capillary Density
 - v. Inflammatory Response
 - vi. Collagen Deposition

Secondary Outcomes:

- a. Complete Wound Closure Rates (defined as 100% epithelialization).
- b. Wound Size Progression Over Time 7 weeks

- c. Number of Reapplications
- d. Incidence of treatment-related adverse events (e.g., infection, allergic reactions)
- e. Quality of Life Improvement
- f. Patient Satisfaction Scores

Study Design

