Randomization and Blinding

Patients will be randomized 1:1 to the HPTC or dHCAM group using a computer-generated randomization sequence. Due to the nature of the interventions, blinding of participants and clinicians is not feasible. However, outcome assessors and data analysts will be blinded to group assignments.

Data Collection and Monitoring

- a. Baseline data: Demographics, medical history, ulcer characteristics.
- b. Weekly follow-ups: Wound measurements (photographic documentation), assess healing progress, record adverse events and patient-reported outcomes.
- c. End-of-Study Visit (Week 5): final wound assessment, collect patient feedback on treatment experience.
- d. Data entry and monitoring will be managed using an electronic data capture system.
- e. Regular monitoring will ensure adherence to the study protocol and address any compliance issues.

Statistical Analysis

Descriptive statistics for baseline characteristics. Statistical analysis was performed using SPSS version 26.0 (IBM Corp., Armonk, NY). Continuous variables were presented as mean \pm standard deviation or median (interquartile range) based on distribution normality assessed by Kolmogorov-Smirnov test. Categorical variables were presented as frequencies and percentages.

Between-group comparisons for continuous variables were performed using independent t-test or Mann-Whitney U test as appropriate. Chi-square test or Fisher's exact test was used for categorical variables. Time-to-event analysis was performed using Kaplan-Meier survival curves with log-rank test. Repeated measures ANOVA was used to analyse wound size changes over time.

Statistical significance was set at p<0.05. All analyses were performed on intention-to-treat basis with last observation carried forward for missing data.

Sample Size Calculation

Sample size calculation was based on expected difference in wound closure rates between groups. Assuming 85% closure rate in HPTC group versus 65% in dHACM group, with 80% power and 5% significance level, 38 patients per group were required. To account for 10% dropout rate, 40 patients per group were enrolled.

Study completion

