Patients will complete the study 6 weeks after the first treatment visit. In addition, if, patients whose study ulcer closes prior to the 6-week visit will be considered as having completed the study. Complete healing of the study ulcer is defined as 100% re-epithelialization without drainage. At any point during the treatment period, patients can refuse to participate or withdraw from the study without prejudice. If a patient withdraws from the study, their last available wound measurement will be carried forward and used to calculate change in wound size and their final outcome

Ethical Considerations

- i. Approval will be obtained from the Institutional Ethics Committee.
- ii. Adherence to the Declaration of Helsinki and Good Clinical Practice (GCP) guidelines.
- iii. Informed and written consent will be obtained from all participants.
- iv. Adverse events will be monitored and reported.
- v. Participants may withdraw at any time without penalty.
- vi. Dissemination of Results
- vii. Findings will be submitted to peer-reviewed journals and presented at relevant conferences.

Timeline

Recruitment: 1 months Intervention: 3 months

Data analysis and reporting: 1 months

Potential Implications

This study aims to provide direct comparative data on the efficacy of HPTC versus dHACM in the treatment of pressure sores. The findings could inform clinical decision-making and potentially lead to improved patient outcomes in wound care management of pressure sores.

References:

- 2. Berhane, C. C., Brantley, K., Williams, S., Sutton, E., & Kappy, C. (2019). An evaluation of dehydrated human amnion/chorion membrane allografts for pressure ulcer treatment: a case series. *Journal of Wound Care*, 28(Sup5), S4–S10. https://pubmed.ncbi.nlm.nih.gov/31067170/
- 3. Vecin, N. M., & Kirsner, R. S. (2023). Skin substitutes as treatment for chronic wounds: current and future directions. *Frontiers in Medicine*, 10, 1154567. https://www.ncbi.nlm.nih.gov/pmc/articles/PMC10498286/
- 4. Helicoll® Clinical Study Publications. [https://helicoll.com/clinical-studies/]
- 5. A Randomized Controlled Clinical Trial Comparing the Use of High-Purity Type I Collagen Matrix (HPTC) and Dehydrated Human Amnion/Chorion Membrane (dHACM) Allografts in the Management of Diabetic Foot Ulcers.

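### All analyses, adverse events included, follow assigned arm and no safety set is defined; wrong-product or untreated patients, if there are any, would shrink the safety difference

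*Combined protocol and SAP*

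**What the plan says.** The only statement of an analysis population is in Statistical Analysis: "All analyses were performed on intention-to-treat basis with last observation carried forward for missing data". Outcome Measures lists as secondary outcome d: "Incidence of treatment-related adverse events (e.g., infection, allergic reactions". A yes/no incidence would be compared under the rule "Chi-square test or Fisher's exact test was used for categorical variables".

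The other references to safety name no population. Data Collection and Monitoring says the weekly follow-ups will "record adverse events and patient-reported outcomes", and Ethical Considerations says "Adverse events will be monitored and reported". There is no safety or as-treated set, and no rule for a patient who receives the wrong product, both products or none. Intention-to-treat itself is not defined.

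On missing data, Study completion says of a patient who withdraws that "their last available wound measurement will be carried forward and used to calculate change in wound size and their final outcome". Randomization and Blinding says "Patients will be randomized 1:1 to the HPTC or dHCAM group" and that "blinding of participants and clinicians is not feasible".

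**The concern.** A treatment-related event is judged against the product that was on the wound, but the plan tabulates it by the product the patient was assigned. The two agree only when every patient receives the assigned product.

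- **Wrong product.** If a patient randomised to HPTC is given dHCAM and reacts to it, the event is counted in the HPTC arm.
- **No product.** A patient who is randomised but never treated cannot have a treatment-related event, yet stays in the denominator.

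Analysis by assignment is the right basis for the efficacy question, where shrinkage toward no difference is the cautious error. For safety, an error in that direction is not cautious. Event counts will be small at 40 per arm, so a single event counted in the other arm can change how the table reads.

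**Working it through.** **The plan's own figures.** The plan gives no adverse event rate, wrong-product rate or never-treated rate, so there is no safety figure to reproduce. Its one computed figure, 38 per group for closure rates of 85% and 65%, plays no part here. The 10% dropout allowance is not a never-treated rate. Study Design gives both 40 per arm and 20 per group; I use 40, which is also the number in Sample Size Calculation.

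**Assumptions.** True event risks by product received are pA = 20% and pB = 5%. In each arm a share u is never treated (zero risk of a treatment-related event) and a share x receives only the other product. The shares are equal in the two arms, and deviating patients carry the same risk as others on the product they receive.

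**Expected rates by assigned arm.**

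- rA = (1 − u − x)·pA + x·pB
- rB = (1 − u − x)·pB + x·pA
- rA − rB = (1 − u − 2x)·(pA − pB)

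With u = x = 5%:

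- rA = 0.90 × 20% + 0.05 × 5% = 18.25%
- rB = 0.90 × 5% + 0.05 × 20% = 5.5%
- difference = 0.85 × 15 = 12.75 points

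With u = x = 10%:

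- rA = 0.80 × 20% + 0.10 × 5% = 16.5%
- rB = 0.80 × 5% + 0.10 × 20% = 6.0%
- difference = 0.70 × 15 = 10.5 points

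**Power.** Exact enumeration of Fisher's test at two-sided 5%. By assignment there are 40 per arm. By product received there are 40(1 − u) per group, at 20% against 5%.

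| u | x | Difference by assignment (points) | Power by assignment | Power by product received |
|---|---|---|---|---|
| 0 | 0 | 15.0 | 41.1% | 41.1% |
| 5% | 0 | 14.25 | 37.9% | 37.9% |
| 10% | 0 | 13.5 | 34.5% | 34.5% |
| 0 | 5% | 13.5 | 32.8% | 41.1% |
| 0 | 10% | 12.0 | 25.4% | 41.1% |
| 5% | 5% | 12.75 | 29.7% | 37.9% |
| 10% | 10% | 10.5 | 19.8% | 34.5% |

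Never-treated patients alone lower both rates in proportion, and leaving them in costs essentially no power compared with leaving them out. Wrong-product use is what costs power.

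**One misplaced event.** Suppose one HPTC-assigned patient received dHCAM and had an event. By product received, 6/41 on dHCAM against 0/39 on HPTC gives Fisher p = 0.026. By assignment, the same data are 5/40 against 1/40, p = 0.20. This example was chosen to straddle 0.05; it shows what can happen, not what is likely.

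**The case against.** The strongest reply is that the harm depends on deviations the documents neither report nor predict. Eligibility is confirmed again before randomisation, and monitoring is meant to secure adherence. Open-label use could prompt deliberate switching, but it also makes accidental misapplication less likely. This stands: the text supports no particular rate, and with full adherence the two analyses are identical.

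Four stronger readings are tempting, and the documents do not support them.

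- **A reader might infer that the plan hides a real safety difference.** That needs wrong-product use, for which there is no rate. At 5% or less of each deviation, the loss is at most 2.25 of an assumed 15 points.
- **A reader might take the power loss as 41% down to 20%.** The 41% belongs to perfect adherence. In the 10%-and-10% case, analysis by product received reaches only 34.5%, so the loss due to the choice of population is 34.5% to 19.8%, about 15 points, with 20% of each arm off plan.
- **A reader might call the outcome definition and the population rule contradictory.** They are not. One is a causality judgement on each event, the other says which patients are counted and where. The gap is a missing specification for safety.
- **A reader might think adverse events are to be carried forward.** The general sentence is loose enough to allow it, but Study completion describes carry-forward only from the wound measurement. This needs clarifying, no more.

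It is also fair to say that sample size limits safety detection more than the analysis set does: power is 41% even with perfect adherence.

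**Conclusion.** The point holds as a conditional weakness that is cheap to remove. The plan states a rule without exception, the rule covers treatment-related adverse events, and no safety set is defined. If patients receive the other product or none, in equal shares across arms, the expected difference shrinks by the factor 1 − u − 2x. That is 15% smaller at 5% and 5%, and 30% smaller at 10% and 10%. The power cost against analysis by product received is about 8 points (30% against 38%) and 15 points (20% against 34%) respectively, and it comes from wrong-product use.

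These sizes rest on assumed rates of 20% and 5%, 40 per arm, and equal deviation shares. With unequal shares the distortion need not be toward zero: 10% untreated in the lower-risk arm alone gives 20% − 0.90 × 5% = 15.5 points. With no deviations the effect is nil. The plan should be changed, but this does not undermine the efficacy analysis.

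**What to change.** Replace the general sentence with text to this effect:

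> Efficacy analyses are by intention to treat. Adverse events are analysed in all patients who received at least one application, by the product actually received; a patient who received both products is counted once, under the product first applied, and is listed separately with the product in place at each event. Last observation carried forward applies to wound measurements only, not to adverse events.

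Keep the adverse event table by assigned arm as support, and report the number of wrong-product and untreated patients in each arm. Counting each patient once keeps the two groups independent, as Fisher's test requires; the listing shows any event that arose on the second product.

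The cost is a few sentences, one extra table, and a record of the product used at each application. The rule should be fixed before events are reviewed by group, because a safety set chosen afterwards is open to challenge. The downside is small: a comparison by product received is not fully protected by randomisation, which is why the assigned-arm table stays. The change does not cure the low power for safety.

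### The only sample size calculation is for complete closure, a secondary outcome; no target difference, SD or power is stated for any primary outcome, so the 80% figure cannot be attached to one

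*Combined protocol and SAP*

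**What the plan says.** In Outcome Measures, the primary outcome has two parts: (a) "Percentage Wound Area Reduction" and (b) histopathological parameters, of which six are listed. The first item under the secondary outcomes is "Complete Wound Closure Rates (defined as 100% epithelialization".

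The Sample Size Calculation section contains the only sizing argument in the document. It opens "Sample size calculation was based on expected difference in wound closure rates between groups", continues "Assuming 85% closure rate in HPTC group versus 65% in dHACM group", and concludes "with 80% power and 5% significance level, 38 patients per group were required". It then adds "To account for 10% dropout rate, 40 patients per group were enrolled".

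Neither the Statistical Analysis section nor any other section gives an expected difference, a standard deviation or a power figure for area reduction or for any histology item. Nothing links the closure calculation to a primary outcome. Neo-epithelialization is in the primary list, but as a tissue parameter. The closure rate is listed separately, as secondary.

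**The concern.** A reader who sees 80% power in a protocol will normally apply it to the primary outcome. Here it was worked out for a different outcome, on a different scale: a proportion rather than a percentage change.

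Two consequences follow. First, a non-significant result for area reduction could be reported as a well-powered negative, which nothing in the plan supports. Second, the outcome list points to area reduction while the design rationale points to closure. If the two results differ, each has some claim to be what the trial was built to test, and in an open-label trial that should be settled before comparative data are seen.

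This is a separate matter from whether 38 per group is the right arithmetic. A correct closure calculation would still be one for a secondary outcome.

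**Working it through.** **Inputs from the document.** Closure 85% versus 65%, 80% power, 5% significance, 38 per group required, 10% dropout, 40 per group (Sample Size Calculation); 1:1 allocation (Randomization and Blinding); "Statistical significance was set at p<0.05" (Statistical Analysis). Sidedness is not stated; I assume two-sided.

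**Step 1. The plan's own figure.** Pooled normal approximation for two proportions, mean proportion 0.75:

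n = [1.960 × √(2 × 0.75 × 0.25) + 0.842 × √(0.85 × 0.15 + 0.65 × 0.35)]² / 0.20²
= [1.960 × 0.6124 + 0.842 × 0.5958]² / 0.04 = 72.4, so 73 per group.

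The stated 38 is not reproduced. Other two-sided forms give 70 (unpooled), 71 (arcsine) and 83 (continuity-corrected); one-sided forms give 55 to 67. The dropout step does not follow either: 38 / 0.90 = 42.2, so 43 rather than 40.

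**Step 2. What the closure calculation delivers.** Power = Φ{[0.20 × √n − 1.960 × 0.6124] / 0.5958}:

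| n per arm | Power, 85% vs 65% |
|---|---|
| 40 | Φ(0.109) = 54% |
| 38 | Φ(0.055) = 52% |
| 36 (40 less 10%) | Φ(0.000) = 50% |

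Exact enumeration at 40 per arm gives 55% for the chi-square test and 46% for Fisher's test.

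**Step 3. What the numbers deliver for a primary outcome.** No required n can be computed, because neither a target difference nor an SD is given. The question can be turned round: what difference does the planned size detect? By the normal approximation, d = (1.960 + 0.842) × √(2/n), which is 0.626 SD at n = 40 and 0.660 SD at n = 36. The t-test versions are slightly larger:

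| n per arm | Detectable difference (SD units) | In points, assumed SD 20 | In points, assumed SD 40 |
|---|---|---|---|
| 40 | 0.634 | 12.7 | 25.4 |
| 36 | 0.670 | 13.4 | 26.8 |
| 20 | 0.909 | 18.2 | 36.4 |

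The last row is shown because Study Design gives 40 per arm and then lists 20 patients in each group. The SDs are my assumption. The figures are for one outcome tested alone at 5%.

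**Step 4. Whether power could be good or poor.** For an assumed difference of 15 points at 40 per arm (normal approximation), power is 99%, 92%, 77%, 61% or 48% for assumed SDs of 15, 20, 25, 30 or 35 points. The answer depends entirely on inputs that the plan does not give.

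**Step 5. The ceiling at 100%.** If 65% to 85% of ulcers close, those patients all have 100% area reduction. Suppose non-closers in both arms have mean reduction m and SD 20 (assumed). The mean difference is 0.20 × (100 − m), and the variance in an arm with closure rate p is (1 − p) × 20² + p(1 − p)(100 − m)².

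- m = 40: difference 12 points; variances 519 and 959; SD √739 = 27.2; standardised difference 0.44.
- m = 70: difference 6 points; variances 174.75 and 344.75; SD √259.75 = 16.1; standardised difference 0.37.

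Both are below 0.634. This is one illustrative model. It shows why the t-test figures in Step 3 are only approximate, and why a continuous scale does not guarantee more power here.

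**The case against.** The strongest reply is that the outcome ranking is explicit, and a sample size rationale does not override a declared primary outcome. The mismatch biases no estimate and changes no procedure. Closure and area reduction are also closely related, so contradictory results are less likely than for two unrelated outcomes. All of this stands. It limits the harm to what the power statement can support and how results may be presented.

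A reader might go further and infer that the trial is underpowered for its primary outcome. The documents do not support that. They give no difference and no SD, and Step 4 shows that 40 per arm could be ample or poor. Power is unstated, which is not the same as absent.

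A reader might also infer that closure should simply be made primary, since the trial was sized on it. That does not follow either. On the plan's own rates closure has about 54% power at 40 per arm, and 73 per arm would be needed before dropout. Moving a registered secondary outcome up could itself be seen as outcome switching: parts of the text are in the past tense, and the documents do not show whether comparative data have been seen.

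Finally, the SD range is assumed, and a t-test on values bunched at 100% is a rough guide; the plan itself allows a Mann-Whitney test. For that reason the detectable differences should be quoted as approximate.

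**Conclusion.** Wrong as written. The stated 80% power concerns a secondary outcome, and none of the seven primary items has a target difference, SD or power. This rests on the text alone and needs no assumption.

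The size of what can be said instead is a detectable difference of about 0.63 SD at 40 per arm, or 0.67 SD at 36, for one continuous outcome at 80% power and two-sided 5%. The conversion to about 13 to 25 points (13 to 27 at 36 per arm) rests on the assumed SD of 20 to 40 points and is approximate because of the ceiling at 100%.

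The 80% figure does not hold for closure either: about 54% at 40 per arm and 50% at 36, two-sided, on 85% versus 65%.

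**What to change.** Keep the declared primary outcome and rewrite the Sample Size Calculation paragraph to say that:

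- the closure calculation concerns a secondary outcome;
- no power was calculated for percentage area reduction or for any of the six histology items;
- 40 per arm detects about 0.63 SD in a single continuous outcome at 80% power, two-sided 5% (0.67 SD with 36 per arm after 10% loss), with the conversion to points given as approximate and the assumed SD shown;
- on 85% versus 65%, power for closure is about 54% at 40 per arm and 50% at 36, so the 80% claim is withdrawn there too.

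The group sizes of 40 and 20 in Study Design must be reconciled first, because these figures assume 40.

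Promoting closure to primary is optional. It should be considered only if the change is documented before any comparative data are seen. It would need the 80% claim withdrawn and the registered outcome order updated. The closure definition would also have to be reconciled (Study completion adds absence of drainage; Outcome Measures does not), as would the assessment time (Week 5 for the end-of-study visit in Data Collection and Monitoring, 6 weeks in Study completion, 7 weeks for wound size progression in Outcome Measures).

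Cost: the main fix is wording only, with no extra patients or data. The downside is a less favourable power statement. Actually reaching 80% power for closure would take more patients: 73 / 0.90 = 81.1, so 82 per arm after 10% dropout.

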Prospective, randomized, controlled, single-centre study with two parallel-group, open-label trial Duration: 6 weeks of intervention with follow-up for 1 week. Participants will be randomly assigned in a 1:1 ratio to receive either HPTC or dHCAM treatment

Sample Size: 80 patients (40 per arm)

- i. Group A: 20 patients receiving HPTC treatment.
- ii. Group B: 20 patients receiving dHCAM treatment.

Eligibility Criteria

Inclusion criteria

- a. Subjects must be at least 18 years of age or older
- b. Presence of a Stage III or Stage IV pressure ulcer, as defined by the National Pressure Ulcer Advisory Panel
- c. Ulcer size between 5 cm² and 25 cm²
- d. Ulcer duration of at least 4 weeks prior to enrolment
- e. The subject must agree to attend the twice-weekly/weekly study visits required by the protocol
- f. The subject must be willing and able to participate in the informed consent process
- g. Adequate blood supply to the affected area, confirmed by clinical assessment

Exclusion criteria

Potential subjects meeting any of the following criteria will be excluded from enrolment.

- a. A subject known to have a life expectancy of <6 months
- b. Presence of infection in the ulcer requiring systemic antibiotics.
- c. Known allergy to components of HPTC or dHCAM.
- d. Participation in another wound care study within the last 30 days.
- e. A subject with autoimmune or connective tissue disorders.
- f. Women who are pregnant or considering becoming pregnant within the next 6 months and those who are breast feeding.
- g. History of autoimmune disease, immunosuppressive therapy, malignancy, or uncontrolled diabetes (HbA1c >10%).

Study treatment

The treatment phase will begin with a series of assessments designed to confirm the patients' continued eligibility. Subjects who continued to meet study inclusion criteria after the screening period were randomized to one of two groups:

- 1. HPTC
- 2. dHCAM

Interventions

Wound Preparation - Prior to application, wounds will be debrided to remove necrotic tissue and cleansed with a standard saline solution.

Application Protocol:

- a. HPTC Group: Participants will receive standard wound care plus application of HPTC
- b. dHCAM Group: Participants will receive standard wound care plus application of dHCAM

All participants will receive standard care measures, including:

- a. Regular repositioning to alleviate pressure.
- b. Nutritional support to address deficiencies.
- c. Management of comorbid conditions.

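### 38 per group does not give 80% power for 85% versus 65% closure: 73 per group are needed, and the planned 40 give about 54%

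*Combined protocol and SAP*

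**What the plan says.** The Sample Size Calculation section bases the trial on complete wound closure: "Assuming 85% closure rate in HPTC group versus 65% in dHACM group, with 80% power and 5% significance level, 38 patients per group" are said to be required. It continues: "To account for 10% dropout rate, 40 patients per group were enrolled". The Study Design section gives the same total, 80 patients with 40 in each arm, and 1:1 allocation, although the two lines below that total list 20 patients per group.

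The Statistical Analysis section says "Statistical significance was set at p<0.05" and "Chi-square test or Fisher's exact test was used for categorical variables". It also names a log-rank test for time-to-event data, and intention-to-treat analysis with the last observation carried forward. Neither section says whether the 5% level is one- or two-sided, or which sample-size formula was used. Under Outcome Measures, complete closure is a secondary outcome; the primary outcomes are percentage wound area reduction and a set of histopathological parameters.

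**The concern.** A 20-point difference between 85% and 65% usually needs around 70 patients per group for 80% power, so 38 looks like roughly half the right number. The step from 38 to 40 also looks too small to absorb a 10% loss.

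If both are wrong, the trial is presented as having 80% power for closure when its chance of detecting the planned difference is close to even. A non-significant result could then be misread as showing that the two products perform alike. No other sample-size argument appears in the document, so nothing else supports the choice of 80 patients.

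**Working it through.** **Inputs.** From Sample Size Calculation: p1 = 0.85, p2 = 0.65, power 80%, significance level 5%, dropout 10%, stated n = 38 and then 40 per group. From Study Design: 1:1 allocation. Two-sided testing is assumed as the conventional reading; one-sided results are shown as well.

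**Attempt to reproduce 38.** The pooled mean is 0.75, and p1(1−p1) + p2(1−p2) = 0.1275 + 0.2275 = 0.355.

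n = [1.96·√(2·0.75·0.25) + 0.8416·√0.355]² / 0.20² = (1.2002 + 0.5015)² / 0.04 = 2.896 / 0.04 = 72.4, so **73 per group**.

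Other versions, per group at 80% power:

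| Method | Two-sided 5% | One-sided 5% |
|---|---|---|
| Pooled variance | 73 | 57 |
| Unpooled variance | 70 | 55 |
| Arcsine | 71 | 56 |
| Continuity-corrected | 83 | 67 |
| Log-rank (exponential closure times assumed, hazard ratio ln 0.15 / ln 0.35 = 1.81) | 60 to 63 | 48 to 50 |

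None gives 38. With 85% in one group, the two-sided pooled formula returns 38 when the other rate is about 56%, a 29-point difference.

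**Dropout step.** 38/0.9 = 42.2, so 43 per group (the shortcut 38 × 1.1 = 41.8 gives 42). Conversely, 40 × 0.9 = 36, below the stated requirement. Going from 38 to 40 covers a loss of 1 − 38/40 = 5%.

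**Power for 85% versus 65%.** At n = 40, z = (0.20·√40 − 1.2002)/√0.355 = (1.2649 − 1.2002)/0.5958 = 0.109, which gives 54.3%. In the same way, and by exact binomial enumeration:

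| n per group | Two-sided, normal approx. | Exact chi-square | Fisher's exact | One-sided 5%, normal approx. |
|---|---|---|---|---|
| 36 | 50.0% | 50.5% | 40.5% | 62.7% |
| 38 | 52.2% | 53.4% | 43.6% | 64.8% |
| 40 | 54.3% | 55.3% | 46.0% | 66.7% |
| 73 | 80.3% | 80.8% | 75.4% | 88.1% |

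A two-sided log-rank test at 40 per group, under the same exponential assumption, has about 63% power.

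**What 40 per group can do.** Two-sided power of 80% is reached for about 85% versus 57%, a 28-point difference. At the planned rates, the 95% confidence interval for the closure difference has half-width 1.96·√(0.355/40) = 0.185, about ±18 points.

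**Effect of withdrawals.** As an illustration, suppose 10% of each arm withdraw with an open ulcer and are carried forward as not closed, and that 85% and 65% are rates among completers. The rates become 0.9 × 85% = 76.5% and 0.9 × 65% = 58.5%, and power at 40 per group is about 40%.

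**The case against.** The strongest counter-argument concerns scope. Closure is a secondary outcome, and the document gives no standard deviation or effect size for the primary outcomes, so their power is unknown and could be adequate. That stands: the 54% is power for closure, not for the trial as a whole. It does not rescue the section, which bases the sample size on closure and offers nothing else.

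Sidedness is unstated, and a one-sided 5% test would have 67% power at 40 per group, which is better than even. That is also true, but it is still short of 80% and still needs 57 per group.

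Under intention-to-treat with the last observation carried forward, all 40 per group are analysed, so 54% is the direct figure; 50% applies only if dropouts are lost. That is accepted. Carrying an open ulcer forward does not restore power, however: it lowers the observed closure rates. The 40% figure rests on equal dropout in both arms and on completer rates, neither of which the document states.

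Finally, the document makes no equivalence or non-inferiority claim, so misreading a null result is a risk and not a certainty.

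**Conclusion.** The stated calculation is wrong as written. From its own inputs the requirement is 73 per group (two-sided 5%, uncorrected chi-square), nearly twice 38, and no formula tried reproduces the stated number. Separately, 40 per group does not cover 10% dropout from 38; 43 would be needed.

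Power for closure at 40 per group is about 54% two-sided (46% with Fisher's exact test), against the 80% claimed, and 50% with 36 evaluable. The percentages depend on the test and on sidedness, but every version examined falls short of 80%. They also assume 40 per group; if the 20 per group listed in Study Design were the real size, two-sided power would be about 30%.

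**What to change.** Rewrite the Sample Size Calculation section as follows.

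- Reconcile the group size with Study Design, where 40 per arm and 20 per group both appear.
- State that the test is two-sided, and name the test for closure.
- Remove the claim that 38 per group gives 80% power. For 40 per group, state about 54% power for 85% versus 65% with the chi-square test, or about 50% with 36 evaluable. If the 28-point difference (85% versus about 57%) is given, label it as the detectable difference at this size and not as a design assumption.
- Remove the claim that 40 allows for 10% dropout.
- Commit to reporting the closure difference with its 95% confidence interval, and state that a non-significant result does not show equivalence.
- Say plainly that closure is a secondary outcome and that no power calculation is given for the primary outcomes.

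This is a change of wording only and needs no extra patients; its price is a less favourable power statement. If 80% power for a 20-point difference is to be kept, the plan needs 73 evaluable per group (146 in total), or 73/0.9 = 81.1, so 82 per group (164 in total), after 10% dropout. If Fisher's exact test is to be used, 73 per group gives only about 75% power, and the continuity-corrected 83 is the better guide.
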